## 11. STUDY POPULATION

Unless otherwise stated, all tables and listings in this section will be based on the All Treated Population, and all summaries and data listings will use treatment labels as specified in [Section 7](#).

### 11.1. Disposition of Subjects

A summary of the number of subjects in each of the analysis populations described in [Section 7](#) will be provided. In addition, the number of subjects enrolled by center will be summarized by treatment group using the All Treated Population. A listing of subjects excluded from analysis populations will also be provided.

A summary of subject status and reason for study withdrawal will be provided. This display will show the number and percentage of subjects who withdrew from the study, including primary reasons for study withdrawal; the number and percentage of subjects who died will also be presented. Reasons for study withdrawal will be presented in the order they are displayed in the eCRF. In addition, a summary table and listing identifying reasons for screening failures will be presented.

A summary of study treatment status will be provided. This display will show the number and percentage of subjects who have discontinued study treatment and a summary of the primary reasons for discontinuation of study treatment. Reasons for study treatment discontinuation will be presented in the order they are displayed in the eCRF. A listing of study treatment discontinuation will be generated. The listing will include last dose date, and reasons for study treatment discontinuation as well as study part and phase of discontinuation.

### 11.2. Protocol Deviations

All protocol deviations will be summarized and listed and will include inclusion/exclusion deviations as well as other deviations.

A separate listing of inclusion/exclusion deviations will also be provided.

### **11.3. Demographic and Baseline Characteristics**

The demographic characteristics (e.g., age, race, ethnicity, sex, baseline height, and baseline body weight) will be summarized and listed. Age, height and weight will be summarized using the mean, standard deviation, minimum, median, and maximum. In addition, age will also be categorized and summarized by 18-64, 65-74, and >74. The count and percentage will be computed for sex and ethnicity. Planned treatment, if different from actual treatment, will be listed in demographic characteristics listing. In addition, for the re-enrolled subjects from Part 1 to Part 2, the information will be indicated in Part 2 demographic characteristics listing.

Race and racial combinations will be summarized and listed. Family history, history of tobacco use and alcohol intake at screening will be listed.

Disease history and characteristics: primary tumor type, histology, histologic grade, HPV status, time since initial diagnosis in months, stage at initial diagnosis, and time from last occurrence will be summarized. Indicators (yes/no) for the following, collected at screening, will also be summarized: measurable disease, non-target lesions, and progression on previous therapy. Medical conditions present at screening will be listed and will be summarized by past and current. Disease history and characteristics, as well as these medical conditions, will be presented in data listings.

Prior anticancer therapy will be coded using GSK Drug coding dictionary and will be classified by type (chemotherapy, immunotherapy, hormonal therapy, biologic therapy, small molecule targeted therapy, and vaccine, etc.). Some prior anticancer therapy may not have type available and will be summarized under “Missing” type. Prior anticancer therapy will be summarized by type of therapy. A subcategory immunotherapy - prior anti PD1/PD-L1 will be included in the summary table as well. A summary of the number of prior anticancer therapy regimens by type will also be produced. Prior anticancer therapy will be listed.

Prior anticancer radiotherapy will be listed. Prior cancer and non-cancer related surgeries will be summarized and listed.

### **11.4. Concomitant Medications**

Concomitant medications will be coded using GSK Drug coding dictionary and listed. Anatomical Therapeutic Chemical (ATC) classification Level 1 (Body System) information will be included in the dataset created but will not appear on the listing or summary.

Blood products or blood supportive care products will be listed.

### **11.5. Subsequent Anticancer Therapies**

Follow-up anticancer therapy will be coded using GSK Drug coding dictionary. A listing of follow-up anticancer therapy will show the relationship between preferred term and verbatim text; therapies will be classified by type (chemotherapy, immunotherapy, hormonal therapy, and biologic therapy, etc.).

On treatment and follow-up anticancer radiotherapy will be listed.

On treatment and follow-up cancer and non-cancer related surgeries, together with prior cancer and non-cancer related surgeries will be summarized and listed.

## 12. EFFICACY ANALYSES

### 12.1. Endpoints / Variables

Tumor response i.e., complete response (CR/irCR), partial response (PR/irPR), and stable disease (SD/irSD), and progressive disease (PD/irPD) will be based on the assessments from the investigators' review of objective evidence (e.g., radiological scan). Overall responses were measured in accordance with the RECIST v1.1 and irRECIST. If the overall response reviewed by investigator is non-radiologic PD per RECIST v1.1 at a time point, the tumor response at that time point will be derived based on the assessments of target lesion, non-target lesion, and new lesion at that time point, using the below logic:

Target Lesion Response Assessment per RECIST v1.1	Non-target Lesion Assessment per RECIST v1.1	New Lesion Assessment per RECIST v1.1	Derived Overall Response per RECIST v1.1
No target lesion at baseline	CR	No	CR
No target lesion at baseline	NON-CR/NON-PD	No	NON-CR/NON-PD
No target lesion at baseline	NE	No	NE
No target lesion at baseline	PD	No	PD
No target lesion at baseline	PD	Yes	PD
No target lesion at baseline	Any	Yes	PD
CR	CR	No	CR
CR	NON-CR/NON-PD	No	PR
PR	NON-CR/NON-PD	No	PR
PR	NE	No	PR
SD	NON-CR/NON-PD	No	SD
SD	NE	No	SD
SD	No non-target lesion at baseline	No	SD
NE	NON-CR/NON-PD	No	NE
NE	No non-target lesion at baseline	No	NE
PD	any	any	PD
any	PD	any	PD
any	any	Yes	PD

ORR, DCR, DOR and TTR will be reported by both RECIST v1.1 and irRECIST.

## 12.2. Summary Measure

The evaluation of anticancer activity will be evaluated based on the All Treated Population as defined in [Section 7](#) unless otherwise specified. Since this is a Phase I study, anticancer activity will be evaluated based on clinical evidence and response criteria. If data warrant, the response data will be summarized by dose level or expansion cohort type.

Lesion assessment method and timing, evaluation of disease, disease progression and response criteria will be conducted according to RECIST (version 1.1) [[Eisenhauer, 2009](#)] and irRECIST as outlined in Appendix 5 of the protocol. irRECIST will be used to determine treatment decisions and will be used for the primary analysis of anticancer activity.

### 12.2.1. Best Overall Response (BOR)

Best response will be summarized. A swimmer plot of study duration and best response will be produced by cohort.

#### 12.2.1.1. Confirmed Best Overall Response (BOR)

The confirmed best overall response is the best confirmed response recorded from the start of treatment until disease progression or start of new anti-cancer therapy, whichever earlier, and will be determined programmatically based on investigator assessment at each time point. Note that if the investigator assessment is non-radiologic PD by RECIST v1.1 at a time point, the overall response will be derived based on the logic specified in [Section 12.1](#). The derived overall response at that time point will be used to derive BOR.

If there are two assessments separated by not evaluable (NE) assessment(s) the best response shall be assessed applying the algorithm below, collapsing data by ignoring NE assessments.

##### ***12.2.1.1.1. Confirmed Best Overall Response per RECIST (version 1.1) Criteria and irRECIST Criteria***

- To be assigned a status of SD/irSD, follow-up disease assessment must have met the SD/irSD criteria at least once after the first dose at a minimum interval of 77 days.
- If the minimum of 77 days for SD/irSD is not met, the best overall response will depend on the subsequent assessments. For example, if an assessment of PD follows the assessment of SD and SD does not meet the minimum time requirement the best response will be PD. Alternatively, subjects lost to follow-up after an SD assessment not meeting the minimum time criteria will be considered not evaluable.
- To be assigned a status of PR/irPR or CR/irCR, a confirmatory disease assessment should be performed no less than 4 weeks (28 days) after the criteria for response are first met.
- Responses of CR/PR, irCR/irPR that do not meet the requirements of confirmed CR/PR, irCR/irPR are still eligible to be considered SD/irSD if it has met the SD/irSD criteria.

### 12.2.1.1.2. Confirmed Best Overall Response per irRECIST Criteria

Besides the principles specified in [Section 12.2.1.1.1](#), the below principle needs to be considered when deriving the confirmed BOR per irRECIST.

- To be assigned a status of confirmed irPD, a confirmatory disease assessment should be performed at the next disease assessment no less than 4 weeks (28 days) after the criteria for irPD are first met.
- irPD will not override a subsequent best overall response of irSD, irPR, or irCR, meaning that irPR or irSD can be assigned (timepoint response or BOR) even if new lesions have not regressed, or if unequivocal progression (non-target lesions) remains unchanged, providing that the criteria for confirmation of irPD are not met.

Confirmed and confirmed BOR per irRECIST (irBOR) takes into account the requirement for confirmation of irCR, irPR, and irPD. If irBOR is irPD and is confirmed consecutively, irBOR will be termed as irCPD.

If irBOR is irPD but not confirmed and there is no subsequent irSD, irPR, or irCR (e.g. NE or lost follow-up), the confirmed and unconfirmed irBOR will be termed as irUPD. If irBOR is irPD but not confirmed and there is no subsequent irSD, irPR, or irCR (e.g. NE or lost follow-up) due to study conclusion, the confirmed BOR will be termed as N/A (not applicable) and the unconfirmed irBOR will be termed as irUPD.

Examples of Scenarios of Assignments of Confirmed/Unconfirmed Best Overall Response Using irRECIST (assuming the adjacent timepoints are 28 days apart at least):

Case	Timepoint Response 1	Timepoint Response 2	Timepoint Response 3	Timepoint Response 4	Timepoint Response 5	Timepoint Response 6	Confirmed BOR	Unconfirmed BOR
1	irSD [1]	irPR	irPR	irCR	irCR	irPD	irCR	irCR
2	irPR	irSD [1]	irPR				irSD	irPR
3	irSD [2]	NE					NE	NE
4	irSD [2]	irCR	irCR	irPD			irCR	irCR
5	irSD	irSD	irSD	irPR			irSD	irPR
6	irPR	irPR	irPD	irPD			irPR	irPR
7	irPD	irPD [4]					irCPD	irCPD
8	irPD [3]	irPD [4]					N/A	irUPD
9	irPD	irSD [1]	irPD				irSD	irSD
10	irPD [4]						N/A	irUPD
11	irSD [2]	irPD [4]					N/A	irUPD
12	NE	irPD [4]					N/A	irUPD
13	irPD	NE	NE	NE	NE	NE	N/A	irUPD

Assume any two adjacent assessments are at least 28 days apart

- [1] Assessment at least 77 days after the first dose
- [2] Assessment less than 77 days after the first dose
- [3] This assessment and next assessment is < 28 days
- [4] Last assessment before the subject died/discontinued from study

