- f. The Survival FU visit should be completed every 12 weeks after documented disease progression (or after initiation of another anticancer treatment). Subjects should be contacted every 12 weeks (± 2 weeks) until death occurs. Upon implementation of Protocol Amendment 4, no future survival follow-up is required.
- g. Dosing of GSK3174998 and pembrolizumab at every 3-week intervals is shown in the Time and Events Table; however, dosing of GSK3174998 may be delayed due to toxicity. During the combination phase, GSK3174998 should be administered first, and pembrolizumab should be administered at least 1 hour and no more than 2 hours following the end of the GSK3174998 infusion. GSK3174998 and pembrolizumab will be dosed for a maximum of 2 years or 35 cycles, whichever comes first. Alternative dosing schedules of GSK3174998 and pembrolizumab may be explored if the data warrants. This will be communicated in writing to sites prior to implementation.
- h. Screening tumor imaging must be obtained within 28 days of the first dose. Tumor imaging will be performed every 12 weeks (± 1 week) until disease progression has been confirmed by irRECIST; Subjects whose disease progresses must have a confirmatory scan performed at least 4 weeks after the date of assessment during which the first indication of PD was demonstrated. Immune-related RECIST will be used to determine treatment decisions for PD and the primary endpoint analysis will use irRECIST. If a subject has achieved a CR or PR in the previous radiologic assessment, a repeat scan should be performed as a part of the confirmation of response, within at least 4 weeks to confirm the response. At the TDV, tumor imaging is only required if the last disease assessment did not show PD and was performed ≥ 6 weeks before TDV. During the DFS FU visits (performed when a subject has permanently discontinued study treatment before disease progression has been documented), tumor imaging will be obtained every 12 weeks (± 1 week) until PD, initiation of a new anticancer treatment, or death, whichever comes first. Pre-baseline scans (within 24 weeks before the baseline scan) may be collected to assess tumor growth rate in selected subjects to support exploratory investigation of tumor growth kinetics. Upon implementation of Protocol Amendment 4, no future disease assessments are required..

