NOTE: Although CT scan is preferred, MRI may be used as an alternative method of baseline disease assessment, especially for those subjects where a CT scan is contraindicated due to allergy to contrast, provided that the method used to document baseline status is used consistently throughout study treatment to facilitate direct comparison.

Confirmation of CR and PR are required per protocol. Confirmation assessments must be performed at least 4 weeks after the criteria for response have initially been met and may be performed at the next protocol scheduled assessment. If a confirmation assessment is performed prior to the next protocol schedule assessment, the next protocol scheduled evaluation is still required (e.g., evaluations must occur at each protocol scheduled time point regardless of unscheduled assessments).

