9.4.2. Secondary Analyses

9.4.2.1. Anticancer Activity Analyses

The All Treated Population will be used for anticancer activity analyses. Since this is a Phase I study, anticancer activity will be evaluated based on clinical evidence and response criteria. If data warrant, the response data will be summarized by dose level. irRECIST is the primary measure of clinical activity for response endpoints; RECIST v1.1 guidelines are used for disease measurements.

If the data warrant, ORR, DCR, TTR, and DOR will be calculated and listed for each subject.

ORR is defined as the percentage of subjects with a best overall confirmed CR or PR at any time as per disease-specific criteria (refer to [Appendix 5](#)). DCR is defined as the percentage of subjects with a confirmed CR + PR at any time, plus SD ≥ 12 weeks.

DOR will be calculated and listed for subjects with a confirmed CR or PR and is defined as the first documented evidence of CR or PR until disease progression or death due to any cause among subjects who achieve an overall response (i.e., unconfirmed or confirmed CR or PR). TTR is defined as the interval from the first dose of study treatment to the date of the first documented CR or PR. DOR and TTR are considered as exploratory endpoints. No summary tables for DOR and TTR will be provided.

Further details will be provided in the RAP.

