12.5.2.2. Immune-Related RECIST Response Criteria

12.5.2.2.1. Evaluation of target lesions

New, measurable ^a lesions	Incorporated into tumor burden
New, nonmeasurable lesions	Do not define progression (but preclude irCR)
irCR	Disappearance of all lesions in two consecutive observations not less than 4 weeks apart. Any pathological lymph nodes (whether target or non-target) must have reduction in short axis to <10 mm.
irPR	≥30% decrease in tumor burden compared with baseline in two observations at least 4 weeks apart
irSD	30% decrease in tumor burden compared with baseline cannot be established nor 20% increase compared with nadir
irPD ^b	At least 20% increase in tumor burden compared with nadir (at any single time point) in two consecutive observations at least 4 weeks apart. In addition to the relative increase of 20%, the sum must also demonstrate an absolute increase of at least 5 mm.

a. Measurable according to RECIST v1.1.

b. Treatment decisions will be based upon the immune-related RECIST criteria.

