12.5.3.1. Evaluation of best overall response

[figure not shown]
The best overall response is the best response recorded from the start of the treatment until disease progression/recurrence and will be determined programmatically by GSK based on the investigators assessment of response at each time point.

- To be assigned a status of SD, follow-up disease assessment must have met the SD criteria at least once after the first dose at a minimum interval of 77 days.
- If the minimum time for SD is not met, best response will depend on the subsequent assessments. For example if an assessment of PD follows the assessment of SD and SD does not meet the minimum time requirement the best response will be PD. Alternatively, subjects lost to follow-up after an SD assessment not meeting the minimum time criteria will be considered not evaluable.

12.5.3.2. Confirmation Criteria:

To be assigned a status of PR or CR, a confirmatory disease assessment should be performed no less than 4 weeks (28 days) after the criteria for response are first met.

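### SAP irRECIST example Case 2 (irPR, irSD, irPR) denies a confirmed irPR that protocol Appendix 5 grants; Case 13 contradicts the SAP's own irUPD rule

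*SAP*

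**What the plan says.** **Protocol.** Appendix 5, Section 12.5.2.2.1, defines the irRECIST categories in one table. irCR is "Disappearance of all lesions in two consecutive observations not less than 4 weeks apart". The irPD row also asks for two consecutive observations at least 4 weeks apart. The irPR row asks for a 30% or greater "decrease in tumor burden compared with baseline in two observations at least 4 weeks apart", without the word *consecutive*. Section 7.2.2 says "Confirmation assessments must be performed at least 4 weeks after the criteria for response have initially been met" and allows the next scheduled scan to serve. Section 12.5.3.2 sets the same 28-day minimum. Section 9.4.2.1 states "ORR is defined as the percentage of subjects with a best overall confirmed CR or PR at any time" and points to Appendix 5.

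**SAP.** Section 12.2 applies "irRECIST as outlined in Appendix 5 of the protocol" and makes irRECIST the primary basis for anticancer activity. Section 12.2.1.1.1 confirms irPR or irCR by an assessment at least 28 days after the criteria are first met. Section 12.2.1.1.2 adds, for irPD only, that confirmation must come at the next assessment.

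The table headed "Examples of Scenarios of Assignments of Confirmed/Unconfirmed Best Overall Response Using irRECIST" then lists 13 cases:
- Case 2 (irPR, irSD, irPR) has confirmed BOR irSD and unconfirmed BOR irPR.
- Case 13 (irPD, then five NE) has confirmed BOR N/A and unconfirmed BOR irUPD.

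The text above the table makes both BORs irUPD when an unconfirmed irPD has no later irSD, irPR or irCR, and it gives NE and loss to follow-up as examples. It reserves N/A for the case where this results from study conclusion, a term the SAP does not define.

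**The concern.** BOR is derived by program, so the programmer must choose between the written rule and the worked example, and for Case 2 they give different answers. The example imposes an adjacency condition on irPR that neither document states. The protocol table uses *consecutive* for irCR and irPD, and the SAP uses *next* for irPD, so both documents state adjacency where they want it.

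SAP Section 12.2.2 requires confirmation for the final ORR. Sections 12.2.3 and 12.2.4.1 admit only confirmed irCR or irPR to the irRECIST TTR and DOR listings. A subject with the Case 2 sequence would therefore leave all three. Protocol Section 4.5.3 reports clinical responses in Part 2A at 0.01 to 0.3 mg/kg, so the confirmation rule is not idle there.

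Case 13 is a smaller matter. Its row is the very situation the irUPD sentence uses as its example, yet it carries the exception's label.

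**Working it through.** **1. Case 2 against the rule.** The table assumes adjacent assessments at least 28 days apart. The two irPRs are two intervals apart: 28 + 28 = 56 days at minimum. Since 56 ≥ 28, both Appendix 5 (irPR row) and SAP Section 12.2.1.1.1 are met, so the confirmed BOR is irPR. The table says irSD.

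**2. All 13 rows under four readings.** The written rules were applied to every row, varying two points: whether irPR confirmation must be consecutive, and whether footnote [4] (last assessment before death or discontinuation) counts as study conclusion.

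| irPR confirmation | Footnote [4] is study conclusion? | Rows where the table and the rules differ (table → derived) |
|---|---|---|
| Any two, ≥28 days apart | Yes | 2 (irSD → irPR), 13 (N/A → irUPD) |
| Any two, ≥28 days apart | No | 2, 13 as above; 8, 10, 11, 12 (N/A → irUPD) |
| Consecutive only | Yes | 13 (N/A → irUPD) |
| Consecutive only | No | 8, 10, 11, 12, 13 (N/A → irUPD) |

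The table's irSD for Case 2 is reproduced only by adding the consecutive condition. Case 13 differs under every reading, because it carries no footnote and NE assessments are ignored, leaving a single unconfirmed irPD. Cases 8 and 10 to 12 depend on the undefined term. SAP Section 5.3 treats ongoing subjects as withdrawn due to study closure, so these rows are ambiguous, not shown to be wrong.

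**3. Can the sequence occur?** Pharmacodynamic-cohort subjects have an extra Week 6 scan. Take irPR on Day 43, irSD on Day 85 and irPR at Week 24 (Day 85 + 84 = Day 169). Day 85 is 84 days after first dose, above the 77-day minimum for irSD. The gap between the irPRs is 169 − 43 = 126 days.

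With assumed tumor burdens, for illustration only:
- Baseline: 100 mm.
- Day 43: 69 mm, a 31% decrease (irPR).
- Day 85: 72 mm, a 28% decrease, and (72 − 69)/69 = 4.3% above nadir (irSD).
- Day 169: 68 mm, a 32% decrease (irPR).

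A 3 mm fluctuation around the 30% threshold decides whether the subject is a responder.

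**4. Size per affected subject.** Confirmed irRECIST ORR falls by 1/n:
- n = 9, treated at 0.03 mg/kg in combination (Protocol 4.5.3): 1/9 = 11.1 points.
- n = 12, the maximum per dose level (Protocol 4.1.1): 1/12 = 8.3 points.
- n = 45, all monotherapy subjects pooled (Protocol 2.3.5): 1/45 = 2.2 points.

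DCR changes by 0, because the tabled irSD meets the 77-day minimum and counts as disease control. Cases 8 and 10 to 13 change ORR and DCR by 0.

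**The case against.** The best defence is that the first scan after a response is the confirmatory scan. Footnote h of the Time and Events Table says "If a subject has achieved a CR or PR in the previous radiologic assessment, a repeat scan should be performed", and Section 7.3.1 asks for a confirmatory assessment at least 4 weeks after the response. In the calendar above, Day 85 is 42 days after Day 43 and so qualifies. It shows irSD, confirmation has failed, and the last irPR is a new response with no follow-up scan. The SAP then lets an unconfirmed irPR count as irSD. The protocol leaves detail to the SAP, and the worked example supplies it.

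That is a coherent rule, and it may be what was intended, but it is not the written one. The protocol passages tell sites when to scan; none says that only the first later scan can confirm, and Section 7.2.2 is permissive about using the next scheduled visit. Protocol Section 9.4 requires departures from its analysis plan to be documented, whereas the SAP says it follows Appendix 5.

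Several limits do stand:
- ORR in Parts 1A and 2A is descriptive, with no hypothesis test.
- Part 2B had no responses.
- Section 4.5.3 does not say whether the Part 2A responses were confirmed, or how many there were at each dose.
- Unconfirmed BOR still shows irPR for Case 2.
- The percentages in step 4 would apply to any single reclassified subject, and the 45-subject pool is not a planned display.
- All five unconfirmed-irPD rows read N/A and irUPD, which suggests study conclusion may have been meant to cover the end of a subject's participation. As printed, Case 13 does not say so.

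**Conclusion.** The concern holds. Case 2 conflicts with the irPR definition in Appendix 5 and applies a condition that SAP Section 12.2.1.1.1 does not contain. The conclusion rests on reading Appendix 5 as written, with the omission of *consecutive* from the irPR row taken as meaningful because the irCR and irPD rows include it. Each affected subject would lower a dose level's confirmed irRECIST ORR by 8.3 to 11.1 points at n = 12 to 9 and would drop out of the TTR and DOR listings. The number affected is unknown and may be zero, and the effect is confined to Parts 1A and 2A.

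Case 13 contradicts the adjacent text as printed. Cases 8 and 10 to 12 cannot be judged until study conclusion is defined. These rows affect BOR labels only. The inconsistencies should be corrected before the final programs are run, but they do not threaten the study's main conclusions.

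**What to change.** 1. In the SAP example table, change the confirmed BOR of Case 2 to irPR. If a consecutive rule is wanted, state it in Section 12.2.1.1.1 and record it as a departure from Appendix 5.
2. Change the confirmed BOR of Case 13 to irUPD.
3. Define study conclusion, and say whether it covers an individual's death or discontinuation. Align Cases 8 and 10 to 12 with that definition: irUPD where death or discontinuation is not due to study conclusion, N/A otherwise.

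The cost is a few table cells and one definition, with no new data. The change belongs before database freeze, so that the rule is chosen without reference to which subjects it reclassifies.
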